4.0 Study Outcomes and Study Measures

We will perform a randomized pilot study comprised of eight groups. All of these groups employ accepted techniques, medications and dressings and therefore are not experimental.

Group 1: Breast skin after mastectomy will be clinically examined by the surgeon to determine if there is adequate blood flow to the skin to allow safe coverage of the breast implant. No dye study, ointment, or vacuum dressing will be applied to the breast after implant placement.

Group 2 - Breast skin after mastectomy will be clinically examined by the surgeon, and nitroglycerin (NTG) cream will be applied to the breast skin after implant placement. This cream does not have systemic effects but may improve blood flow to the remnant breast skin after mastectomy.

Group 3 - Breast skin after mastectomy will be clinically examined by the surgeon, and an incisional vacuum-assisted dressing (iVAC) will be placed over the breast incisions after implant placement, which may improve blood flow to the skin and help wound healing.

Group 4 - Breast skin after mastectomy will be clinically examined by the surgeon, and both NTG cream will be applied to the breast skin and an iVAC will be placed over the incisions after implant placement.

Group 5 - Blood flow to breast skin after mastectomy will be examined using a fluorescent dye study called fluorescent angiography (FA) to determine if there is adequate blood flow to the skin to allow safe coverage of the breast implant. No further intervention will be used after implant placement.

Group 6 - Blood flow to breast skin breast skin will be examined using FA, and NTG cream will be applied to the skin after the implant is placed.

Group 7 - Blood flow to breast skin breast skin will be examined using FA, and an iVAC will be placed over breast skin incisions after the implant is placed.

Group 8 - Blood flow to breast skin breast skin will be examined using FA, and both NTG cream and iVAC will be used as interventions after the implant is placed.

The dosage of indocyanine-green (IC-green) to be used for assessment of mastectomy flaps will be in 10 mg boluses, not to exceed 5 mg/kg.

Nitro-Bid® (nitroglycerin ointment, 2%) at a dose of 45 mg (equal to 7.5 cm on the measuring strip provided with packaging) will be used. The paste will be applied to remnant breast skin after skin closure and surgical dressings placed over top.

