5.1 Study Related Activities

Potential subjects will be identified by the physician, advanced practice provider, or research coordinator. This individual will discuss the study with the patient and answer any questions or concerns they may have. This will take place in an exam room, hospital room, or by phone depending on whether or not the patient is inpatient or a clinic patient.

Signed informed consent will be obtained from each subject who will be undergoing mastectomy with immediate breast reconstruction using breast implants during a pre-operative appointment in the General Surgery (Breast Oncology) or Plastic Surgery clinic. After the subject has been identified as meeting the inclusion criteria by the clinician or research coordinator, the study coordinator will obtain the signed informed consent. A signed copy of the consent form will be given to the subject. Once the patient has agreed to take part in the study and sign the consent form, pre-operative photos of the breast will be taken. Pregnancy tests performed 15 days apart (prior to surgery) is done as standard of care for all women of childbearing age potentially undergoing this surgery.

Twenty subjects will be randomized to each arm of the study using sealed instructions provided by the study coordinator who will inform the clinician of the arm prior to surgery. The envelopes will be filled prior to the study with envelopes containing a document indicating to which group the patient will be a part of. The envelopes will be sealed and shuffled and then labeled from subject 1 through 160.

Once the subject is randomized to an arm of the study, the operating surgeon will be informed of the arm prior to the surgery. On the day of surgery, the surgeon will decide intraoperatively whether an implant/tissue expander can be safely placed without compromising perfusion of the flap. If the surgeon determines that an implant/tissue expander cannot be safely placed, they will continue to be followed as that indicates a perfusion related problem. At that point, another envelope will be introduced into the pre-made envelopes with that subject’s assigned arm. Pictures will be take pre-

The Effect of Nitroglycerin Ointment, Fluorescent Angiography, and Incisional NPWT on Mastectomy Skin Flap Perfusion-Related Problems Comprehensive Cancer Center of Wake Forest University (CCCWFU)

PI: [name] IRB #00038262 NCT03716050 Date of Document: 05/07/2019

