operatively, intraoperatively, and at week 1,2,3, and 4 post-operatively. In addition to these pictures, the data collecting sheet will be completed by the physician, advanced practice provider or study coordinator at week 1, 2,3 and 4 post-operatively.

This is not an intent-to-treat trial. In order to ensure that we are able to gather the most information from this study, we want to be able to closely monitor our enrolled subjects and remove any subjects that are non-compliant with their randomized arm. The study coordinator will be responsible for keeping a detailed Excel spreadsheet of the enrolled subjects and their respective arms of the study. If a subject comes off the study prematurely, another envelope will be introduced to the pre-made envelopes with the withdrawn subject's arm – in this way the arms will never be unbalanced.

This study will be monitored by the Cancer Center's Safety and Toxicity Review (STRC) for SAEs and will also be monitored for accrual by the Clinical Research Oversight Committee (CROC) since this is an institutional intervention study. The standard operating procedures for the STRC can be found below in appendix c.

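### Section 5.1 rejects intention-to-treat and removes and replaces undefined non-compliers, with no all-randomised analysis planned, so arm-level complication rates may describe a selected subset

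*Combined protocol and SAP*

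**What the plan says.** Section 5.1 states: "This is not an intent-to-treat trial". The team intends to "remove any subjects that are non-compliant with their randomized arm". When a subject leaves early, an envelope for the same arm is added, on the reasoning that "in this way the arms will never be unbalanced".

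The documents do not define non-compliance. They do not say who decides on removal, up to what point, or whether the decision may be made knowing the outcome. The arm is not concealed from the people involved: "the operating surgeon will be informed of the arm prior to the surgery", and the study coordinator, who holds the allocation list, may also complete the weekly outcome sheet.

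Section 8.3.1 plans outcome rates with 95% confidence intervals but names no analysis population. Section 8.1.1 aims for 20 completed subjects per arm. The only quantity given an all-accrued denominator is attrition (Section 8.3.2).

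Some provisions limit the problem:

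- Of subjects in whom no implant can be placed, Section 5.1 says "they will continue to be followed as that indicates a perfusion related problem".
- "The study coordinator will be responsible for keeping a detailed Excel spreadsheet of the enrolled subjects and their respective arms".
- Deviations go to the IRB (Section 6.0).
- Dropout and its reasons are reported by group (Sections 8.0 and 8.3.2).

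**The concern.** Randomisation makes the arms comparable at entry. Removing subjects afterwards, for a reason that may be tied to arm or outcome, can undo that. A replacement restores the count but not the outcome of the subject who left.

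The documents give two reasons to think removal could be selective. First, the arms differ in what there is to comply with. In Group 1, "No dye study, ointment, or vacuum dressing will be applied to the breast after implant placement"; in Group 8, which also has the dye study, "both NTG cream and iVAC will be used as interventions after the implant is placed". Second, Section 4.0 lets the physician give whatever therapy is judged necessary at the weekly visits and puts the subject's well-being above the assigned arm. Section 5.1 does not say whether such a departure counts as non-compliance. If it does, a subject treated for a developing PRP could be taken out of the arm's rate.

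The rates matter because Section 8.0 uses them to design a larger trial, Section 2.0 aims to compare the interventions, and Section 8.3.1 gives power for comparisons of 80 versus 80.

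**Working it through.** **The plan's own figures.** Section 8.1.1: 8 × 20 = 160, and 160 × 1.15 = 184, or 23 per arm. (Dividing by 0.85 gives 189; the difference does not matter here.) The nine power rows in Section 8.3.1 reproduce by exact enumeration of the pooled Z test. The exact interval for 10/20 is 27.2% to 72.8%, which is the stated ±22.8 points. The arithmetic is sound; the question is who is counted.

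**Inputs.** The 10% and 20% rates are from the Section 8.3.1 tables. The removed share *m* is an assumption: 15% borrows the dropout figure of Section 8.1.1 only as a scale, and 5% is a lower case. The ratio *k*, the removal rate in PRP subjects relative to others, is also an assumption.

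**Formula.** With true rate *r*, subjects without a PRP are removed with probability *q* and those with one with probability *kq*. Then *m* = (1 − r)q + rkq, so

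- q = m / (1 − r + rk)
- observed rate = r(1 − kq) / (1 − m)

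**One arm, r = 0.10, m = 0.15.**

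- k = 2: q = 0.15/1.10 = 0.1364; observed = 0.10 × (1 − 0.2727)/0.85 = 8.6%.
- k = 4: q = 0.15/1.30 = 0.1154; observed = 0.10 × (1 − 0.4615)/0.85 = 6.3%.
- k = 1: 10.0%, no bias.
- k = 0.5: 10.8%. k = 0: 11.8%.

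**Two groups, true 10% v 20%, a difference of 10 points.** In the last two columns removal is related to outcome in one group only, with k = 1 in the other.

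| Removed | k | 10% seen as | 20% seen as | Difference, same k in both | 10% group only | 20% group only |
|---|---|---|---|---|---|---|
| 15% | 2 | 8.6% | 17.6% | 9.1 | 11.4 | 7.6 |
| 15% | 4 | 6.3% | 14.7% | 8.4 | 13.7 | 4.7 |
| 5% | 2 | 9.6% | 19.3% | 9.7 | 10.4 | 9.3 |
| 5% | 4 | 8.9% | 18.4% | 9.5 | 11.1 | 8.4 |

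The distortion is small when removal acts alike in both groups and larger when it differs between them.

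**Effect on planning the larger trial.** Per-group size from the pooled-variance two-proportion formula, assuming two-sided 5% and 80% power:

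n = [z₀.₉₇₅√(2p̄(1 − p̄)) + z₀.₈₀√(p₁(1 − p₁) + p₂(1 − p₂))]² / (p₁ − p₂)²

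| Scenario (k = 2) | Same in both groups | 10% group only | 20% group only |
|---|---|---|---|
| True rates, no selection | 199 | 199 | 199 |
| 15% removed | 216 | 146 | 319 |
| 5% removed | 204 | 181 | 226 |

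**Logical bounds.** With 23 randomised, 20 retained with 2 PRPs and 3 removed with unknown outcome, the all-randomised rate lies between 2/23 = 8.7% and 5/23 = 21.7%. Any three missing outcomes would give the same bounds.

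**Sampling error for scale.** The exact 95% CI for 2/20 is 1.2% to 31.7%. At 80 v 80 with 10% v 20%, the half-width is 1.96 × √(0.10 × 0.90/80 + 0.20 × 0.80/80) = 11.0 points.

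**The case against.** The opening for selective removal is narrow. The dye study is done in the operating room, the ointment goes on after skin closure, and only the vacuum dressing clearly continues, in hospital and for at most 4 days. Most departures would therefore come before the week 1 outcome sheet. The most obvious outcome-related departure, an implant that cannot be placed, is already followed and treated as a PRP.

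The sizes rest on assumptions, some of them strong: k = 4 with 15% removed means about 46% of an arm's PRP subjects are taken out, which nothing in the documents suggests. Sampling error exceeds the largest illustrated distortion (10 − 4.7 = 5.3 points) even at 80 v 80. Section 8.3.1 estimates rates and sets no decision rule. Section 5.1 does not say that data already collected on removed subjects will be discarded, and defining non-compliance and reporting both populations might be enough.

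Much of this stands, and it limits the severity. It does not answer the central point. Early ischaemia could still lead to a departure from the assigned treatment, no cut-off for removal is set, and therapy given at weekly visits is left open. The safeguards show who left, from which arm and why; none guarantees an outcome for those removed. A confidence interval does not reflect selection. As to which population should be primary, only the all-randomised set keeps the protection of randomisation, and the compliant-set analysis need not be lost.

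**Conclusion.** The concern holds. The plan states a removal rule that can bias the arm rates, gives no definition to constrain it, and plans no outcome analysis of everyone randomised. Whether bias occurs, and in which direction, cannot be determined from the documents; it requires removal to be related to outcome, and it distorts comparisons most when that relation differs by arm. In the assumed scenarios with outcome-related removal at 2 to 4 times the usual rate, a 10-point difference appears as anything from 4.7 to 13.7 points with 15% removed, and from 8.4 to 11.1 points with 5% removed. Because this is an estimation pilot whose sampling error is larger than these shifts, the point should be fixed but does not invalidate the study. It is time-sensitive: outcomes not collected after removal cannot be recovered at analysis.

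**What to change.** - In Section 5.1, delete the statement rejecting intention-to-treat and the rule removing non-compliant subjects.
- Collect outcomes to week 4 for every randomised subject unless consent is withdrawn.
- In Section 8.3.1, make PRP rates by assigned arm in all randomised subjects the main analysis. Add a compliant set, defined in advance and independently of outcome, as secondary.
- Report non-compliance and withdrawal by arm, with reason, timing and outcome status.
- Let added envelopes supplement the subjects already randomised, not replace them.
- Reconcile three provisions: the priority of well-being over the arm (Section 4.0), continued follow-up without an implant (Section 5.1) and the removal rule (Section 5.1). State whether such departures count as non-compliance.

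The cost is protocol wording, a short definition, and a compliance and reason field on the data sheet if it has none. Weekly visits are already standard of care, and about 184 subjects are already planned, so no added recruitment is needed within that figure. There are two small downsides: extra data sheets and photographs for subjects who would have been removed, and some dilution of the contrast by non-compliers, which the secondary analysis would show.

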5.2 Duration of Follow-up

Patients will be followed for a minimum of 30 days after the procedure. Clinical assessments will occur weekly.

6.0 Adverse Events List and Reporting Requirements

Any unanticipated problems, serious and unexpected adverse events, deviations or protocol changes will be promptly reported by the principal investigator or designated member of the research team to the IRB and sponsor or appropriate government agency if appropriate.

6.1 Adverse Event Characteristics

Adverse events may include, but are not limited to: anaphylaxis/urticarial reaction, dizziness, light-headedness, blurred vision, fainting, severe allergic reactions (rash, hives, itching, difficulty breathing, tightness in chest, swelling of mouth, face, lips, throat or tongue), flushing and red, swollen, blistered or peeling skin, intraoperative or immediately postoperative/post-procedure death.

6.2 WFUHS IRB AE Reporting Requirements

Any unanticipated problems involving risks to subjects or others and adverse events shall be promptly reported to the IRB, according to institutional policy. Reporting to the IRB is required regardless of the funding source, study sponsor, or whether the event involves an investigational or marketed drug, biologic or device. Reportable events are not limited to physical injury, but include psychological, economic and social harm. Reportable events may arise as a result of drugs, biological agents, devices, procedures or other interventions, or as a result of questionnaires, surveys, observations or other interactions with research subjects.

The Effect of Nitroglycerin Ointment, Fluorescent Angiography, and Incisional NPWT on Mastectomy Skin Flap Perfusion-Related Problems Comprehensive Cancer Center of Wake Forest University (CCCWFU)

PI: [name] IRB #00038262 NCT03716050 Date of Document: 05/07/2019

All members of the research team are responsible for the appropriate reporting to the IRB and other applicable parties of unanticipated problems involving risk to subjects or others. The Principal Investigator, however, is ultimately responsible for ensuring the prompt reporting of unanticipated problems involving risk to subjects or others to the IRB. The Principal Investigator is also responsible for ensuring that all reported unanticipated risks to subjects and others which they receive are reviewed to determine whether the report represents a change in the risks and/or benefits to study participants, and whether any changes in the informed consent, protocol or other study-related documents are required.

Any unanticipated problems involving risks to subjects or others occurring at a site where the study has been approved by the WFUHS IRB (internal events) must be reported to the WFUHS IRB within 7 calendar days of the investigator or other members of the study team becoming aware of the event.

Any unanticipated problems involving risks to subjects or others occurring at another site conducting the same study that has been approved by the WFUHS IRB (external events) must be reported to the WFUHS IRB within 7 calendar days of the investigator or other members of the study team becoming aware of the event.

Any event, incident, experience, or outcome that alters the risk versus potential benefit of the research and as a result warrants a substantive change in the research protocol or informed consent process/document in order to insure the safety, rights or welfare of research subjects.

7.0 Data Management

Race Verification Form	ORIS
Protocol registration form	ORIS
Data Collection	REDCap

8.0 Statistical Considerations

This investigation will be designed as a pilot study, in which patients will be randomized to one of the eight groups described. Once enrollment goals are met, outcomes data will be calculated for each of the primary and secondary measures. Using these estimates, a larger randomized clinical trial will be designed to assess differences between study groups. It is anticipated that the rate of study completion will be uniformly high across the study groups, with low rates of attrition. For use in designing a future trial, we will calculate the rate of dropout for each group. Reasons for dropout will be recorded and reported.

8.1 Estimated Accrual Rate

8.1.1 We anticipate enrolling approximately 70-80 patients per year; With 8 study groups, with 20 subjects per group, the study will need 160 subjects to meet recruitment goals. We will allow for attrition in our enrollment estimates, as our goal is to have 20 completed subjects in each arm. Assuming a 15% dropout rate,

The Effect of Nitroglycerin Ointment, Fluorescent Angiography, and Incisional NPWT on Mastectomy Skin Flap Perfusion-Related Problems Comprehensive Cancer Center of Wake Forest University (CCCWFU)

PI: [name] IRB #00038262 NCT03716050 Date of Document: 05/07/2019
 the study would need approximately 184 subjects. Study recruitment should be completed within 2.5 years.

8.2 Estimated Study Length

8.2.1 The time Follow up time for each patient will be thirty days, which will allow enough time for mastectomy flap necrosis to develop.

8.3 Statistical Analyses

8.3.1 Estimates of all primary outcomes (Soft tissue ischemia/loss, surgical site infection, delayed wound healing) and secondary outcomes (rate of operative intervention, rate of prescribing antibiotics or admission for IV antibiotic therapy, wound care management modalities and outcomes) will be calculated. These data will provide estimates of rates for each outcome that will allow planning for future studies. The rates of the primary outcomes will be reported, along with corresponding 95% confidence intervals. With an anticipated sample size of 20 in each group, the width of the exact 95% confidence interval would be approximately +/- 22.8 if the observed rate was 50%. The table below shows the power for testing against an observed rate of 10% (the anticipated average rate in the 8 study groups) in group 1 versus 20%, 30%, 40%, and 50% in other groups with an alpha of 0.20. With group sample sizes of 20 in each of the 2 groups, the study would have 84% power to detect a difference of 30%.

Numeric Results of Tests Based on the Difference: P1 - P2

H0: P1 - P2 = 0. H1: P1 - P2 = D1 ≠ 0. Test Statistic: Z test with pooled variance

Power	N1	N2	N	Trt H1	Cntrl	Diff	Target	Actual
				P1	P2	D1	Alpha	Alpha
0.36453	20	20	40	0.10	0.20	-0.10	0.2000	0.1966
0.62930	20	20	40	0.10	0.30	-0.20	0.2000	0.2228
0.84713	20	20	40	0.10	0.40	-0.30	0.2000	0.2172
0.95746	20	20	40	0.10	0.50	-0.40	0.2000	0.1920

The table below shows the target and actual alpha and power if groups are combined to have 80 subjects in each one.

Numeric Results of Tests Based on the Difference: P1 - P2

H0: P1 - P2 = 0. H1: P1 - P2 = D1 ≠ 0. Test Statistic: Z test with pooled variance

Power	N1	N2	N	Trt H1	Cntrl	Diff	Target	Actual
				P1	P2	D1	Alpha	Alpha
0.42287	80	80	160	0.10	0.20	-0.10	0.05	0.0503
0.71633	80	80	160	0.10	0.25	-0.15	0.05	0.0518
0.90284	80	80	160	0.10	0.30	-0.20	0.05	0.0513
0.97682	80	80	160	0.10	0.35	-0.25	0.05	0.0507
0.99617	80	80	160	0.10	0.40	-0.30	0.05	0.0472

With group sample sizes of 80 in each of the 2 groups, being compared, the study would have 90% power to detect a difference of 20%.

The Effect of Nitroglycerin Ointment, Fluorescent Angiography, and Incisional NPWT on Mastectomy Skin Flap Perfusion-Related Problems Comprehensive Cancer Center of Wake Forest University (CCCWFU)

PI: [name] IRB #00038262 NCT03716050 Date of Document: 05/07/2019

8.3.2 The rate of attrition and reason for dropout will be reported for each of the study groups; these data will be used in adjusting the needed sample size for a larger study. The rate of attrition and its corresponding 95% confidence interval will be calculated; attrition will be defined as the number of subjects who do not attend the final assessment, divided by the number accrued into the treatment group.

APPENDIX A: REDUCED REVIEW REGISTRATION FORM**

Protocol#: 00038262

*Required Field

Protocol Title: The Effect of Nitroglycerin Ointment, Fluorescent Angiography, and Incisional NPWT on Mastectomy Skin Flap Perfusion-Related Problems CCCWFU#00038262

DEMOGRAPHICS

Name (last, first) : _____, _____
(or initials)

UNIT # (MRN): _____ (required if exists) Zip Code: _____ (required if no MRN)

*SEX { } MALE () FEMALE

*ETHNICITY (choose one): () HISPANIC { } NON-HISPANIC

*RACE (choose all that apply): WHITE ASIAN
 AFRICAN-AMERICAN PACIFIC ISLANDER
(HAWAIIAN)
 NATIVE AMERICAN (ALASKAN) Unknown (Other, Refused}

*DIAGNOSIS : _____

BIRTH DATE: _____ (include if no MRN is provided)

*MD Name (last, first): _____

*DATE CONSENT WAS SIGNED: _____

Date of Registration (if different): _____

PID#: _____ (to be completed by Registrar)

The Comprehensive Cancer Center requires that all registrations be sent to the CCCWFU Centralized Registrar the day the patient is consented; if this is not possible we require that all registrations be communicated to the Centralized Registrar within 72 hours of consent.

**Reduced review means eligibility and other review are not performed by CRM registrar. Questions: call [name]
Submit by Email*** Print Form

*** If not using the full wfubmc edu outlook client (full outlook, not web outlook), save this file and attach to an email to [contact]
Submitter of this form is responsible for insuring that all regulatory and eligibility requirements are met for this registration.

The Effect of Nitroglycerin Ointment, Fluorescent Angiography, and Incisional NPWT on Mastectomy Skin Flap Perfusion-Related Problems Comprehensive Cancer Center of Wake Forest University (CCCWFU)

PI: [name] IRB #00038262 NCT03716050 Date of Document: 05/07/2019

